KØBENHAVNS UNIVERSITET - TANDLÆGESKOLEN

Forsøgsprotokol Jf. GCP-enhedens protokolvejledning

(The main research protocol is developed based on the guidelines for Good Clinical Practice (GCP))

1. Title:

DIMOH: New **Di**gital **M**ethods for **M**onitoring **O**ral **H**ealth. An i*n vivo* assessment. Odontologisk Institut - Tandlægeskolen Det Sundhedsvidenskabelige Fakultet Københavns Universitet [name]

2. Objectives

The objectives of this study are *i*) to monitor the oral health of young people over a period of 12 months and *ii*) to assess the ability of a new intraoral scanner combining fluorescence (from emitted blue light) with 3D imaging to detect and monitor changes in the dental hard tissues *in vivo*.

a. Hypotheses

The working hypotheses of this study are:

- 1. The monitoring of oral health will benefit from using a new intraoral scanner combining fluorescence with 3D imaging.
- 2. The new intraoral scanner combining fluorescence with 3D imaging will aid dentists to identify changes in the dental hard tissues at earlier stages than the traditional diagnostic methods (*i.e.* visual-radiographic methods).

b. Background

Literature Review and Research Question

Currently, monitoring oral health relies mainly on the visual examination of the oral tissues by the dental professional, aided electively by radiographic or photographic images (1, 2). In the context of oral health, monitoring involves detecting changes, sometimes rather subtle, in the soft or hard oral tissues; such changes are associated with the development of oral diseases or ageing (3, 2). Through the course of their lives, people will experience changes in the level of gingiva, increments on the teeth surface due to calcification of biofilm, loss of mineral tissues due to caries or tooth wear, wear of restorative materials, or modification in the in the position or color of the teeth. The slow rate of change involved in some of these situations makes it extremely difficult for the human eye alone to identify them. It is even more challenging to accurately register and recall the original situation on the patient's follow-up visits. Clinical photographs are therefore used to aid the monitoring (4, 2); however, it is difficult to obtain comparable photographs from different points in time and the subjectivity involved in the process cannot be avoided.

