The current 3D intraoral scanners capture the color of the oral tissues by emitting visible white light. A recently developed 3D intraoral scanner manufactured and CE marked by 3Shape A/S. Denmark, is also able to emit visible blue light (405 nm wavelength) (17) that allows capturing fluorescence from the oral tissues. Fluorescence is one of the most promising technologies for accurate detection of the early stages of enamel demineralization (18, 19, 20), but is currently available only in 1D or 2D devices. The main limitation of the existing devices featuring fluorescence, as already mentioned, is the challenge in comparing single images obtained at different points in time, which is at large influenced by imaging artifacts and noise. Imprecision in the comparison of these images compromises the ability to accurately monitor progressive demineralization of the dental hard tissues. To the best of our knowledge, there is no intraoral scanner reported in the scientific literature that combines fluorescence with 3D imaging. Thus, we hypothesize that this new intraoral scanner will benefit the monitoring of dental hard tissues and will aid dentists to identify early changes in tissue mineralization. With this method it is only possible to examine the tooth surfaces that are visible and directly exposed into the mouth (i.e. the smooth free surfaces and the occlusal fissures); the areas between the teeth (i.e. the approximal surfaces) cannot be visualized and therefore cannot be examined using the scanner.

3. Methods

Study execution

The participants will be monitored for a period of 1 year. The study will last approximately 2 years in total, with the baseline examination taking place in the beginning of 2019 and the last examination in the Spring – Winter 2020. Detailed plan of the study is shown in Table 1.

Information about the project

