A second appointment will be scheduled to conduct the oral health examination, including intraoral scanning and 2 bitewing radiographs (BW). The responsible researcher will request the participants to provide any recently available BW, in case these are not older than 6 months. No study-related examination will be conducted before the signed parental consent form has been obtained by the responsible researcher. The participants will not be offered any treatment other than routine professional tooth cleaning, which is important for a thorough visual examination and scanning of the teeth. In case any oral disease is detected, the participants will be referred to their dentist for treatment.

If no radiographs are available from the past six months, BW of the upper and lower posterior teeth on both sides will be taken. Since radiographs are part of the participants' annual dental check-up, these will be made available to the participants' dentist. Additionally, an oral examination will be conducted, and the condition of teeth, gums and fillings will be registered. The approximal plaque accumulation will be registered by employing the approximal plaque index (21). Thereafter, the teeth will be professionally cleaned, and the presence of caries lesions will be registered based on the visual and radiographic assessments. Caries lesions will be characterized as active or inactive and classified according to the ICDAS criteria into 7 stages (22). Furthermore, the presence of other visible defects on the oral hard tissues (*i.e.* erosive – abrasive lesions) will be registered using appropriate criteria (*i.e.* BEWE index for erosive tooth wear) (2, 23).

Subsequently, both the upper and lower jaw of the participant will be scanned using the intraoral scanner (Trios 4, 3Shape Trios A/S, Denmark). Scans will be obtained using visible white and blue light (wavelength 415 nm).

At the end of the session, the participants will be classified into different risk groups (low, moderate, high) according to the clinical findings and the information collected from the diet

history and the oral hygiene habits questionnaire (Appendix 1, 2). According to this classification, the responsible researcher will set the follow-up intervals for each participant (3-12 months). All patients will be monitored for 1 year.

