The same clinical procedures will be followed on the follow-up examinations (3 or 6 months) as well as on the final examination (1-year follow-up). The diet history, the oral hygiene habits questionnaire and the BW radiographs will be repeated only on the final examination (Table. 1).

4. Statistics

Paired T-test will be conducted to identify differences between the clinical scores at the baseline and the subsequent follow-ups for the different conditions investigated (*i.e.* caries score, erosion score) (24).

Exploratory analysis of the data extracted from the 3D scans will be conducted and compared to the clinical scores. Pearson correlation coefficients between the clinical scores and scores obtained from the 3D scans will be calculated. Paired t-test will be conducted to compare the number of lesions per patient (*i.e.* caries, tooth wear) that will be detected with the 2 different methods (scanning and clinical-radiographic examination).

All statistical analysis will be conducted using a 95% level of confidence.

Information regarding the sample size calculation using power analysis is provided on the following paragraph (§5. Research subjects - Sample size calculation)

5. Research subjects

The participants in this research project will be adolescents (12-16 years old) and young adults (18-19 years old) in Denmark and in Greece respectively.

As previously mentioned, this project will assess the ability of the intraoral scanner combining fluorescence to detect and monitor initial changes in the dental hard tissues, with special focus on caries: the most prevalent oral disease. The most important benefit expected by using the fluorescence method is the detection of initial lesions on dental surfaces directly exposed to the mouth. Fissure lesions in permanent posterior teeth usually appear in the long-lasting period of tooth eruption, *i.e.* from when the tooth first appears in the mouth until it contacts with the opposite dentition (28). Eruption of the first permanent molar starts around the ages of 6-8 years, the second molar at 12-14 years (28) and the third molar at 17-18 years. During the eruption period, the posterior teeth are at a higher risk for developing fissure caries. For the second permanent molars, this period can last up to 27 months form the first appearance in the mouth (~12 years old) (29) though for the third molars this period is usually longer.

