The initial state of the caries lesion is short-lived before progression of the disease. In older patients, caries lesions in fissures are either found at more advanced stages or they have already been treated by the dentist (*i.e.* sealed, filled or extracted as in the case of third molars) (28). Although initial caries lesions can be found in older patients, such initial lesions are located on the surfaces between the teeth, which are not visible to the intraoral scanner and therefore cannot be detected using this method.

For these reasons, the age group is set from 12 to 19 years. It is necessary to conduct the study on this group of young people, as the study is expected to benefit them directly. The same benefits are not expected if the study is conducted in older adults.

The early diagnosis of initial lesions in the young participants is more beneficial as it will allow the implementation of preventive measures to stop the progression of the disease. This will decrease the complexity of the treatments needed in the target group, as the initial lesions can be treated with minimal or non-invasive approaches. Thus, the economic burden for the state regarding treatment expenses of the adolescents and the individual costs related to future dental treatment will be reduced.

Inclusion criteria:

- Young people (12-19 years old) without chronic diseases.

Exclusion criteria:

- Participants in need of complex dental treatment (*e.g.* extensive restorative work, extractions, prosthetic treatment).
- Participants using partial/complete removable dentures or other appliances (*i.e.* orthodontic devices).

Sample size calculation

Caries data was used in order to calculate the desirable sample size for the current study, as that is the most prevalent oral disease in young patients and is widely investigated in epidemiological studies (1). Therefore, data regarding initial caries lesions was used for the sample size calculation, assuming that the new method will aid dentists to detect significantly more initial caries lesions compared to traditional methods.

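### Pearson r on scores of unstated unit and scale, plus a t-test on patient totals, will not show same-surface and same-stage agreement between scanner and examination

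*Combined protocol and SAP*

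**What the plan says.** Section 4 (Statistics) introduces the scanner analysis with "Exploratory analysis of the data extracted from the 3D scans will be conducted and compared to the clinical scores". It then names two between-method statistics:

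- For the scores themselves: "Pearson correlation coefficients between the clinical scores and scores obtained from the 3D scans will be calculated".
- For lesion totals, as a second comparison: "Paired t-test will be conducted to compare the number of lesions per patient", the two methods being scanning and the combined clinical and radiographic examination.

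The other paired t-test in section 4 compares clinical scores over time, not methods. Nowhere do the documents plan a surface-by-surface cross-classification, a kappa or another agreement measure.

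Four other places bear on this:

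- Objective ii (section 2) is the scanner's ability "to detect and monitor changes in the dental hard tissues", and hypothesis 2 (section 2a) expects changes to be found "at earlier stages than the traditional diagnostic methods".
- Section 3 (Clinical and radiographic examination) has caries lesions "classified according to the ICDAS criteria into 7 stages". The scale of the scan score is not given.
- Section 2b (Background) says that the surfaces between the teeth "cannot be visualized and therefore cannot be examined using the scanner". Section 4 does not limit either comparison to the surfaces the scanner can see.
- Section 5 (Sample size calculation) says that "data regarding initial caries lesions was used for the sample size calculation". Section 4 does not say which stages count as a lesion in the t-test.

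**The concern.** Objective ii is about detection at particular sites, and hypothesis 2 is about stage. The informative result is therefore which surfaces are flagged by both methods, by the scan only or by the examination only, and whether the scan stage is higher, equal or lower. A correlation of patient totals can be high because some patients simply have more disease, with little overlap in the surfaces flagged. A correlation of surface scores can be high although the two methods never give a lesion the same stage. In either case a favourable coefficient could be reported as support for the scanner without bearing on what the objective asks. Lesions on approximal surfaces, if left in the clinical total, would also enter the comparison as disagreement the scanner cannot avoid.

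**Working it through.** The plan gives no figure for agreement, so everything below rests on assumed data. From section 5 it takes only 64 participants, a mean of 3.08 initial lesions and an SD of 1.23.

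**1. Patient unit, constructed totals.** Assume 64 patients with 60 visible surfaces each and lesion totals drawn with mean 3.08 and SD 1.23.

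| Totals (clinical / scan) | Patient-level r | Mean difference | Clinical lesions also flagged by scan (same / independent / disjoint sites) |
|---|---|---|---|
| 191 / 191 | 1.00 | 0 | 191 / 15 / 0 of 191 |
| 191 / 263 | 0.73 | 72/64 = 1.125 | 100% / 8% / 0% |

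Within each row, r and the t-test are identical whichever sites are flagged.

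**2. Patient unit, methods sharing only the patient's risk.** With 60 surfaces and p = 3.08/60 = 0.0513, the binomial variance is 60 × 0.0513 × 0.9487 = 2.92 (SD 1.71). For a between-patient SD s, the within-patient correlation is ρ = (s²/2.92 − 1)/59. Then patient-level r = 60ρ/(1 + 59ρ), surface-level r = ρ, and the share of one method's surfaces also flagged by the other is p + ρ(1 − p).

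| s (assumed) | ρ = surface-level r | Patient-level r | Shared surfaces |
|---|---|---|---|
| 2 | 0.006 | 0.27 | 6% |
| 3 | 0.035 | 0.69 | 8% |
| 4 | 0.076 | 0.83 | 12% |

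If half the surface results are instead common to both methods, patient-level r becomes 0.5 + 0.5 × (value above). At s = 2 that is about 0.64, with 0.5 + 0.5 × 0.057 = 53% of surfaces shared. A patient-level r of roughly 0.65 to 0.7 is thus compatible with 8% or with 53% of surfaces shared. A surface-level r would tell these apart. The documents' own SD of 1.23 is below the binomial 1.71, leaves no room for shared risk, and gives r of about 0 in this bounding case.

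**3. Surface unit, one-stage shift, no detection error.** Assume the scan uses the clinical scale and scores every lesion one stage higher. With stages 0 to 5 at 80/8/6/3/2/1%:

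- Clinical score X: mean 0.42, mean square 1.16, variance 1.16 − 0.1764 = 0.9836.
- Scan score Y: mean 0.42 + 0.20 = 0.62, mean square 1.16 + 0.84 + 0.20 = 2.20, variance 2.20 − 0.3844 = 1.8156.
- Covariance: (1.16 + 0.42) − 0.42 × 0.62 = 1.3196.
- r = 1.3196/√(0.9836 × 1.8156) = 0.987.
- Exact agreement among lesions: 0%.
- Linear weighted kappa: 1 − 0.20/0.893 = 0.78, where 0.893 is the mean absolute difference expected by chance.

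Four other mixes were tried: 80/12/5/2/0.7/0.3, 80/5/8/4/2/1, 80/6/6/4/2/2 and 95/2/2/0.6/0.3/0.1. Over all five, r is 0.982 to 0.991 and weighted kappa 0.73 to 0.80, against 1.00 for both without the shift. The count of any lesion is unchanged. The count of initial lesions falls by 29% (17 to 12) to 62% (13 to 5) if initial means stages 1–2, or by 11% (19 to 17) to 25% (16 to 12) if it means stages 1–3.

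**4. Surface unit, imperfect detection.** Assume the examination detects 80% of lesions with 1% false positives, the scanner 90% with 2%, errors are independent given the true stage, and false positives are scored stage 1. At 20% prevalence:

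- Flagged by both: 0.20 × 0.80 × 0.90 + 0.80 × 0.01 × 0.02 = 0.1442.
- Flagged by either: 1 − (0.20 × 0.20 × 0.10 + 0.80 × 0.99 × 0.98) = 0.2198.
- Shared: 0.1442/0.2198 = 66%. Scan only: (0.196 − 0.1442)/0.2198 = 24%. Clinical only: (0.168 − 0.1442)/0.2198 = 11%.

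Without a shift, the 66% shared are also in exact agreement. With the full shift only joint false positives agree: 0.00016/0.2198 = 0.1%.

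| Five mixes | No shift | Half of lesions shifted | All shifted |
|---|---|---|---|
| r | 0.78–0.82 | 0.78–0.80 | 0.79–0.81 |
| Exact agreement, affected surfaces | 47–66% | 24–33% | about 0% |
| Linear weighted kappa | 0.71–0.80 | – | 0.56–0.63 |

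If the scanner's false positives are shifted as well, r is 0.74 to 0.80 and weighted kappa 0.52 to 0.62. The reading is the same.

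**The case against.** The strongest replies are these.

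- **Pearson may be run per surface.** A reader might infer that Pearson cannot reveal same-surface disagreement at all. The documents do not support that. The unit is unstated, and at surface level r falls to 0.006 to 0.076 when only patient risk is shared. In steps 3 and 4, r is high because the methods do largely flag the same surfaces; what r misses there is stage.
- **The t-test is not empty.** A reader might infer that nothing planned shows direction. The t-test shows net direction and addresses the sample-size assumption that the scanner finds more initial lesions. In step 4 the any-lesion totals differ by 17% (0.196 against 0.168), and by 29% at 5% prevalence (0.064 against 0.0495). In step 3 a count of initial lesions would reveal the shift; a count of any lesion would not.
- **The harm is hypothetical.** Nothing in the documents suggests a one-stage shift, says that the scan score uses ICDAS or BEWE, or gives between-patient SDs of 2 to 4. An r of 0.27 at SD 2 would mislead nobody.
- **The analysis is exploratory**, and further statistics are not ruled out.

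All four stand as limits on the claim. They do not supply the missing unit, scale or lesion threshold, nor any named analysis of where and how the methods disagree.

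**Conclusion.** The point holds in a limited form. If the unit is the patient, neither named statistic shows whether the methods flag the same surface. If the unit is the surface, r carries information on location but changes by no more than about 0.02 under a uniform one-stage shift (up to about 0.04 if false positives shift too), while exact agreement goes from 47–66% to about 0%. These sizes rest wholly on assumed stage mixes, error rates and SDs. They show what the statistics can miss, not what this study will find.

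Two stronger conclusions might be drawn and should not be. The documents give no ground for removing Pearson; adding the table is enough. Nor would the table establish diagnostic accuracy: no independent reference standard is described, so scan-only lesions could be true early lesions or false positives. Since the scan analysis is labelled exploratory, this is a change that should be made, not one on which the study depends.

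**What to change.** In section 4, state the unit and scale of each scan score and which stages count as a lesion in the t-test.

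Where scan and clinical scores share a scale and are stored per surface, add a paired surface-level cross-tabulation of clinical by scan score, limited to surfaces the scanner can examine (approximal surfaces excluded). Report, with patient-cluster bootstrap 95% intervals:

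- exact agreement among surfaces affected by either method;
- direction: scan only / both / clinical only, and scan higher / same / lower;
- weighted kappa.

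Pearson may stay as secondary. For continuous scan outputs, such as fluorescence or volume, keep a correlation with the same cluster bootstrap. A table of change from baseline to 12 months is optional and should be descriptive only, because misses and false positives at either visit look like change.

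The cost is a few sentences and a little programming, with no new visits or participants. The documents do not say that scores, BEWE in particular, are kept per surface; where they are not, the table cannot be built. Kappa depends on prevalence, and at 0.73 to 0.80 under a noise-free full shift it can look acceptable alone, so it must be read with exact agreement and direction. Low agreement does not by itself mean scanner error, since the scanner is expected to find more.

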For the sample size calculation, data collected by the Central Odontology Register of the Danish National Board of Health (Sundhedsstyrelsens Centrale Odontologiske Register SCOR) during the year 2017 from municipal dental clinics at 98 different municipalities in Denmark was used. According to the data, an average of 3.08 initial lesions, with a standard deviation of 1.23 were identified on 15-year old patients at the different municipalities. In this study, the desirable power was set on 90%, the level of significance on 5% and the effect size on 30% (1 lesion). By applying these parameters, the sample size was calculated to be 64 adolescents. Nevertheless, as a 10% drop-out is expected for this type of study, the final number of participants to be included in the study should be 70.

6. Risks, side effects and shortcomings in short and long term

Risks

This study will be conducted on healthy persons, on whom the procedures followed in this study are assumed to have a negligible risk.

No risk is related to the clinical visual examination.

Regarding the 3D intraoral scanning procedure, if the scan quality is poor and thus the scan is not useful for the research objectives, the scanning procedure should be repeated. This is of no risk for the patient but represents the inconvenience of a delay of the dental visit.

For the scanning using blue light (wavelength 415nm) possible risks exist. For the participant, light irritation of the mucosa and lips may result from a local, acute overexposure to the strong blue light. This irritation, though, is mild and temporary. For the operator, possible harm to the eyes, especially on the lenses and the retinal tissues, may be caused by long-term cumulative exposure to blue light. These risks are not particular for this specific intraoral device but are

common to any dental equipment that uses blue light. Having these risks in mind, the equipment will be used properly and with care: the exposure time will be limited to 15 seconds per tooth and direct exposure to mucous membranes will be avoided. The equipment will be started only after it has been inserted into the patient's mouth. The operator will avoid looking directly into the mouth and instead will look on the computer screen during the scanning procedure. Eye-protection goggles filtering light under 500 nm are suggested to be used by the operator.

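### Pearson correlation is planned between ordered clinical scores and a scan score with no defined scale; a rank correlation with a participant bootstrap would suit these data better at almost no cost

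*Combined protocol and SAP*

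**What the plan says.** Section 4 (Statistics) introduces the scan analysis with "Exploratory analysis of the data extracted from the 3D scans will be conducted and compared to the clinical scores" and then names the measure: "Pearson correlation coefficients between the clinical scores and scores obtained from the 3D scans will be calculated". A blanket sentence follows: "All statistical analysis will be conducted using a 95% level of confidence". No interval method for the correlation is given.

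The clinical scores are described in section 3, under the clinical and radiographic examination. Caries lesions are "classified according to the ICDAS criteria into 7 stages", and erosive wear is recorded with the "BEWE index for erosive tooth wear". Section 4 itself gives caries score and erosion score as its examples of clinical scores.

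The plan does not say what the scan score is, on what scale it is measured, or whether the correlated pair is a surface, a tooth or a participant. Lesion counts are dealt with separately: "Paired t-test will be conducted to compare the number of lesions per patient" detected by the two methods.

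**The concern.** Pearson's r measures straight-line association between two numerical scales. An ICDAS code is a rank: nothing in the plan says that the step from stage 1 to 2 equals the step from 5 to 6. If the scan score is a signal such as fluorescence intensity or loss, a ratio, or a logarithm of either, r differs between those choices even though the ordering of the lesions is identical. The choice is left to the exploratory analysis, so the same scans could yield a strong or a modest correlation depending on a decision that need not be made before the data are seen.

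A second, conditional issue concerns precision. The usual interval for r (Fisher's z) relies on bivariate normal data. If most scores sit at low stages, a few participants with high scores dominate r, and that interval can be too narrow.

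The correlation is the only named statistic that relates scan scores to clinical scores, so it bears on the study's second objective, the scanner's ability to detect and monitor hard-tissue change.

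**Working it through.** **Plan's own figure.** The plan gives no target, precision or power for the correlation. The only figure that can be recomputed is the sample size in section 5 (SD 1.23, difference 1 lesion, 5% significance, 90% power). A two-sided, two-group formula gives 4 × (1.960 + 1.282)² × 1.23² / 1² = 63.6, that is 64 in total, as stated. It is used below only to set n = 64.

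**Check 1: dependence on scale.** The stage mix is an assumption: stages 0 to 6 with probabilities 0.50, 0.20, 0.18, 0.07, 0.03, 0.01, 0.01. The scan signal is taken as b^stage, a perfect, strictly increasing function of the clinical stage.

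- Mean stage = 0.20 + 0.36 + 0.21 + 0.12 + 0.05 + 0.06 = 1.00.
- Mean squared stage = 0.20 + 0.72 + 0.63 + 0.48 + 0.25 + 0.36 = 2.64, so the variance is 1.64 and the SD 1.281.
- For b = 2 the mean signal is 0.50 + 0.40 + 0.72 + 0.56 + 0.48 + 0.32 + 0.64 = 3.62. The mean squared signal is 67.54, so the variance is 67.54 − 3.62² = 54.44 and the SD 7.378. The mean of stage × signal is 0.40 + 1.44 + 1.68 + 1.92 + 1.60 + 3.84 = 10.88.
- Covariance = 10.88 − 1.00 × 3.62 = 7.26, and r = 7.26 / (1.281 × 7.378) = 0.77.

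The same steps for the other values of b:

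| Fold rise per stage | Mean signal | SD of signal | Covariance | Pearson r | Spearman |
|---|---|---|---|---|---|
| 1.5 | 1.783 | 1.457 | 1.706 | 0.91 | 1 |
| 2 | 3.62 | 7.378 | 7.26 | 0.77 | 1 |
| 3 | 16.76 | 76.74 | 58.36 | 0.59 | 1 |
| 4 | 67.54 | 419.5 | 280.1 | 0.52 | 1 |

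The effect does not need a perfect relation. With a latent correlation of 0.7 and an assumed 7-stage clinical score, r is 0.637 on the latent scan scale b and 0.637 after the linear change 10b + 3. It is 0.554 after exp(b), 0.463 after cubing and 0.221 after exp(2b). Spearman is 0.650 in all five cases.

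**Check 2: interval coverage.** The simulation used n = 64 with one independent pair per participant and a latent bivariate normal cut into stages. The interval is atanh(r) ± 1.96/√(64 − 3), and coverage is for the population Pearson r. All the score distributions are assumptions.

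| Score distribution on both methods | Non-zero latent correlation | Coverage of nominal 95% |
|---|---|---|
| Symmetric, 7 stages | 0.3-0.9 | 93.8-94.7% |
| 40/20/15/10/7/5/3% | 0.3-0.9 | 89.7-92.7% |
| 50/20/18/7/3/1/1% | 0.5-0.9 | about 87-90% |
| 80% at stage 0 | 0.3-0.9 | 66-84% |

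At zero correlation coverage is about 95% in every case, including the most skewed. Under-coverage therefore needs both skew and a real association.

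**Check 3: the rank alternative.** An analytic 95% interval for Spearman (Bonett-Wright) in the 40/20/15/10/7/5/3% case covered 94.5% and 94.9% at latent correlation 0.5 and 0.7, where Pearson covered 91.7% and 91.0%. With 80% at stage 0, Spearman also fell short, at 87.1% and 83.2%, against 74.2% and 69.2% for Pearson.

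**The case against.** The plan labels the scan analysis exploratory, and the sample size rests on detecting lesions, not on this correlation. The plan says only that coefficients will be calculated. Fisher's z is not mentioned, and the sentence on 95% confidence may mean no more than the 5% significance level used in section 5. A test of no association keeps its level, because coverage is nominal at zero correlation. If the scan score turns out to be graded in stages like the clinical one, the multiplicative example does not apply as it stands. Spearman also leaves the scan score undefined and measures association, not agreement. All of this stands, and it keeps the point small.

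Two stronger readings are tempting. A reader might infer that Pearson's r is planned on skewed lesion counts. The documents do not support that: counts per patient are assigned to the paired t-test.

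A reader might also infer that the 95% interval for r will fail. That needs marked skew, which the documents do not show. The inclusion criterion, "Young people (12-19 years old) without chronic diseases", does not select for caries, so a pile-up at low stages is plausible. But people needing complex dental treatment are excluded, which tends to remove the most diseased. The one spread given (mean 3.08, SD 1.23 initial lesions) is for counts and may describe variation between municipalities, so it settles nothing about the stage scores.

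What the objection does not remove is the scale problem. It needs no assumption about skew, only ordered codes and an undefined scan scale, and both are in the plan.

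**Conclusion.** The point holds as a minor one. Pearson's r is an ill-suited main measure for ordered ICDAS and BEWE codes against a scan score of unspecified scale, because its value depends on code spacing and on any non-linear choice of scan scale. In the worked example an identical, perfect ordering gives anything from 0.91 down to 0.52. Those values rest on an assumed stage mix and assumed signal growth; that r moves under non-linear recoding does not.

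The loss of interval coverage is conditional: about 87-90% under the assumed mix at latent correlation 0.5-0.9, and close to 95% with symmetric scores or no correlation. The documents do not show which case will apply. The sample size and the paired comparison of lesion counts do not depend on this correlation.

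**What to change.** In section 4, replace *Pearson correlation coefficients* with *Spearman rank correlation coefficients, with 95% intervals from a bootstrap that resamples participants*. Keep Pearson's r, if wanted, only as a secondary description.

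The cost is one sentence and a few lines of code, with no new data. The drawbacks are modest. The rank correlation is not expressed on the raw score scale, and its interval will usually be wider. It describes association and does not show that the two methods agree. If most scores are zero, its intervals may still fall short of 95%, so the share of zeros should be reported beside it.
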